5.3 Lifestyle Considerations

5.3.1 Meals and Dietary Restrictions (Visit 2)

- 1. Children will not be allowed to eat or drink (except water) from 4 hours before dosing until 35 minutes after dasiglucagon administration.
- 2. 35 minutes after dosing, children will be allowed to eat and drink moderately (appropriate to their body size, with a maximum of 50 grams carbohydrates) to minimize discomfort in terms of potential nausea. 2 hours after dosing, children can eat and drink their usual meals. The amount and type of food and drink consumed will be recorded.

5.3.2 Activity

3. Children should remain in bed, to the extent possible, from approximately 30 minutes before hypoglycemia induction until completion of the test procedure 300 minutes after dosing (bathroom visits are allowed).

5.4 Screen Failures

Screen failures are defined as patients who consent to participate in the clinical trial but are not subsequently eligible for the trial. A minimal set of screen failure information is required to ensure transparent reporting of screen failure patients to meet the Consolidated Standards of Reporting Trials publishing requirements and to respond to queries from regulatory authorities. Minimal information includes demography, screen failure details, eligibility criteria, and any SAE. The reason for screen failure must be captured in the eCRF.

Individuals who do not meet the criteria for participation in this trial (screen failure) may be rescreened if investigator judges that rescreening is appropriate due to inclusion or exclusion criteria that may have changed. Rescreening may only be performed once.

5.5 Criteria for Temporarily Delaying Enrollment and Administration of Trial Intervention

Each child may have their dosing visit rescheduled within the visit window for Visit 2 with an additional 21 days compared to Visit 1 (thus the maximum time interval between Visit 1 and Visit 2 will be 50 days + 21 days) due to the following circumstances:

- If the patient has taken any prohibited medication prior to the dosing visit (Visit 2)
- If transient illness means that the patient cannot attend the planned dosing visit (Visit 2)
- If the patient cannot attend the planned dosing visit (Visit 2) due to logistical reasons
- If the target plasma glucose cannot be achieved on the dosing day (Visit 2) while inducing hypoglycemia

6 TRIAL INTERVENTION(S) AND CONCOMITANT THERAPY

Trial intervention is defined as any investigational intervention(s), marketed product(s), or medical device(s) intended to be administered to a trial patient according to the trial protocol.

6.1 Trial Intervention(s) Administered

Zealand Pharma A/S

The IMP of 0.6 mg/0.6 mL dasiglucagon, will be supplied by the sponsor and delivered in a pre-filled syringe. Only eligible children may receive dasiglucagon. Dasiglucagon will be prepared for administration by a designated person at the clinical research site and will be administered by authorized site staff as a SC injection into the buttocks.

The pre-filled syringe does not have a scale. Therefore, administration of 0.3 mg/0.3 mL dasiglucagon requires additional preparation, where dasiglucagon will be transferred into a sterile vial and the volume needed in order to administer 0.3 mL will be drawn into a syringe. The needle used for administration will match the needle of the pre-filled syringe (27G, ½ inch). Needle, syringe, and vials will be supplied by Zealand Pharma. Separate Instructions for Use included in the Trial Materials Manual will describe preparation and administration of the 0.3 mg/0.3 mL dose.

The IMP must be visually inspected prior to administration. The solution should appear clear, colorless, and free from particles. If the solution is discolored or contains particulate matter, do not use. The dose (0.3 or 0.6 mg), date and time of each dose administered will be recorded in the source documents.

[figure not shown]

Table 6-1 **Identification of Trial Intervention**

	Investigational medicinal product	Background intervention	CGM
Intervention Name	Dasiglucagon Apidra®		Dexcom 6
Active Substance	Dasiglucagon	insulin glulisine	Not applicable
Туре	Drug	Drug	Device
Dose Formulation	Liquid formulation, 0.6 mL	Liquid formulation, dose according to weight (see Section 6.5.1)	Not applicable
Unit Dose Strength(s)	0.6 mg/0.6 mL	100 units/mL	Not applicable
Dosage Level(s)	Single dose	Continuous infusion	Not applicable
Route of Administration	Subcutaneous injection	IV	Not applicable
Use	Experimental	Background intervention	Diagnostic
IMP and NIMP/AxMP	IMP	NIMP	Not applicable
Sourcing	Provided centrally by the sponsor	Provided by investigator	Provided centrally by the sponsor
Packaging and Labeling	Single use pre-filled syringe. Each pre-filled syringe will be labeled as required per country requirement	Apidra [®]	Dexcom 6 (manufacturer: Dexcom) will be provided by sponsor

Abbreviation: CGM=continuous glucose monitoring; IMP=investigational medicinal product; IV=intravenous; NIMP=non-investigational medicinal product

6.1.1 Medical Devices

- No sponsor manufactured stand-alone medical devices (or devices manufactured for sponsor by a third party) are provided for use in this trial.
- Glucose analyzer: Glucose analyzers available at the sites will be used to sample plasma glucose.
- CGM tracing: Dexcom G6 Continuous Glucose Monitoring System will be used to sample glucose levels and will be provided by the sponsor for use in this trial. Sponsorprovided Dexcom 6 devices must be used for all patients. The CGM device will be fitted at the site after attending Visit 2 and at least 2 hours before the planned hypoglycemia induction. The Dexcom G6 CGM will usually require a 2-hour warm-up period to acclimatize before the sensor reading will start. The hypoglycemia induction should not start until the sensor warm-up period is completed and data is received from sensor. All patients must remain fitted with the CGM until 300 minutes after IMP administration. Patients will be under medical supervision at all times while the device is in use. For the purpose of this trial, the device may be used outside the intended purpose for patients

below 2 years (approval applies to 2 years and older). No mechanical or design changes have been made to the device. The CGM device is used as intended according to the CE mark and the 510K clearance, except for using it in patients below the approved age of 2 years.

EAL&

- For interstitial glucose data generated by the Dexcom G6 CGM System, the investigator will ensure that CGM data are downloaded from the device at Visit 2.
- Instructions for medical device use are provided by the manufacturer of the medical
 device. The Dexcom G6 System should be used according to the manufacturer's
 instructions; it does not require calibration. The contract research organization (CRO) or
 delegate will handle the sourcing, configuration for use in the trial, procedures for data
 extraction, service, and return handling for the Dexcom G6 System.
- All technical complaints regarding the dasiglucagon pre-filled syringes shall be
 documented and reported by the investigator throughout the trial (see Section 8.3.9) and
 appropriately managed by the sponsor.

6.2 Preparation/Handling/Storage/Accountability

Dasiglucagon must be stored in a refrigerator (36°F to 46°F/2°C to 8°C). The investigator or designee must confirm that appropriate conditions including temperature conditions have been maintained during transit to and storage at site for all dasiglucagon received and any discrepancies are reported and resolved before use of dasiglucagon.

All dasiglucagon must be stored in a secure, environmentally controlled, and monitored (manual or automated) area in accordance with the labeled storage conditions with access limited to the investigator and authorized site staff.

The investigator or designee is responsible for dasiglucagon accountability, reconciliation, and record maintenance (ie, receipt, reconciliation, and final disposition records). Each pre-filled syringe will have a trial unique dispensing unit number (DUN), which is to be used for traceability purposes.

Further guidance and information related to handling and preparation of dasiglucagon including supply ordering, assignment of dasiglucagon, handling of temperature excursions, and final disposition of used/unused dasiglucagon are provided in the Trial Materials Manual (TMM).

6.3 Trial Intervention Compliance

Patients are dosed at the site, they will receive dasiglucagon injection directly from the investigator or designee, under medical supervision. The dose (0.3 or 0.6 mg) and date and time of each dose administered will be recorded in the source documents. The dose of dasiglucagon and trial patient identification will be confirmed at the time of dosing by a member of the trial site staff other than the person administering the trial intervention.

6.4 Dose Modification

No dose modification is planned for this trial.

6.4.1 Retreatment Criteria

No retreatment criteria are planned for this trial.

All patients entered into the trial will be treated at Visit 2. If the target plasma glucose cannot be achieved on the dosing day during the induced hypoglycemia procedure, the patient can be rescheduled as described in Section 5.5.

6.5 Treatment and Dosing Conditions

Patients will be admitted to the clinic with their parent(s)/legal guardian(s) the night before or at early morning of the dosing day (Visit 2). The patient's eligibility will be checked.

The CGM device will be fitted at the site after attending Visit 2 and at least 2 hours before the planned start of the hypoglycemia induction. The Dexcom G6 CGM will usually require a 2-hour warm up period to acclimatize before the sensor reading will start. The hypoglycemia induction should not start until the sensor warm up period is completed and data is received from sensor. All patients must remain fitted with the CGM device until 300 minutes after IMP administration.

For patients on multiple daily injection insulin therapy

For patients on multiple daily injections (MDI), insulin therapy will be adjusted at the discretion of the investigator in the days prior to the dosing visit (Visit 2) with the purpose of having as low as ambient insulin exposure during the intervention period on Day 1 as possible. During the period with adjusted insulin treatment, the safety of the patient will be ensured by frequent plasma glucose monitoring and contact with the clinical site, as needed. Details (insulin, dose level and timing) regarding the patient's regular insulin therapy and the insulin therapy in the days prior to the dosing visit (visit 2) will be captured in the eCRF for the individual patient.

[figure not shown]
For patients on insulin pump therapy

For patients on insulin pump therapy, the patient's insulin pump is stopped approximately 1 hour prior to dosing in the morning of Day 1, Visit 2.

Details (insulin, dose level and timing) regarding the patient's insulin therapy will be captured in the eCRF for the individual patient.

6.5.1 Hypoglycemic Clamp Procedure and Dosing

Hypoglycemia induction will be initiated using IV insulin to target a plasma glucose level between 70 and 90 mg/dL (between 3.9 and 5 mmol/L).

Version 6.0, 12 Jul 2024

Insulin (only insulin glulisine [Apidra®] will be used) will be provided by the investigator. Insulin infusion for IV use will be prepared according to the patient's body weight at the dosing visit.

Preparation of the insulin infusion:

- 0.5 international units insulin glulisine (Apidra®) per kg body weight
- 48 mL NaCl 0.9%

Zealand Pharma A/S

Plasma glucose must be checked using glucose analyzer before initiation of induction of hypoglycemia. Hypoglycemia will be induced using insulin IV infusion rates according to plasma glucose levels according to Table 6-2.

Table 6-2 Insulin Infusion Rates

Glucose	Infusion rate	Insulin dose (IU/kg BW/h)
>200 mg/dL	10.0 mL/h	0.1
150-200 mg/dL	5.0 mL/h	0.05
90–149 mg/dL	2.5 mL/h	0.025
<90 mg/dL	Insulin infusion stop!	0

Abbreviations: BW=body weight; IU=International units

The procedure to induce hypoglycemia is given as a guidance and any deviation to increase or decrease the insulin rate is allowed at the discretion of the investigator. If the target plasma glucose cannot be achieved on the dosing day, the patient can be rescheduled for another visit as described in Section 5.5.

During the induction phase (during insulin infusion) and following the administration of dasiglucagon, glucose levels will be monitored by both CGM and by a glucose analyzer (see Section 6.1.1). Plasma glucose levels should preferably be checked by glucose analyzer approximately every 10 minutes while glucose levels are above 110 mg/dL (6.1 mmol/L), and preferably approximately every 5 minutes once glucose levels are at or below 110 mg/dL (6.1 mmol/L). Plasma glucose should be confirmed by the glucose analyzer prior to the administration of dasiglucagon. After dosing with dasiglucagon, once glucose levels reach ≥110 mg/dL (6.1 mg/dL), glucose levels should preferably be checked approximately every 30 minutes until 300 minutes. The monitoring frequency of plasma glucose via the glucose analyzer should be adjusted as needed based on the child's body weight to ensure that a maximum of approximately 1.5% is obtained during the dosing visit as specified in Section 6.5.3 (1.5% equals 1.13 to 1.20 mL/kg with the total blood volume estimated to be 75 to 80 mL/kg).⁵

[figure not shown]
At the discretion of the investigator, additional plasma glucose measurements can be taken at any time during the trial, for example when there is a suspicion (eg, symptoms) of a hypoglycemic episode.

A catheter (eg, an indwelling catheter) will be inserted into the child's arm for blood draw for PK/PD sampling. If possible, the same IV access as used for insulin infusion can be used for the PK/PD sampling to reduce the stress and discomfort for the child. Attention should be made to ensure blood samples will be collected from the circulating blood volume and not from a reservoir dead space created by the catheter. If direct venipunctures are considered more appropriate, especially for those children where the number of PK and PD samples are reduced (refer to Table 6-4), venipunctures can be used instead of indwelling catheters. The catheter will be placed in the morning prior to IMP administration. Blood samples for baseline assessment of plasma glucose and dasiglucagon PK will be collected approximately 5 minutes after the glucose concentration reaches >70 mg/dL and < 90 mg/dL (3.9 to 5.0 mmol/L). These samples are the baseline samples and should be collected within 2 minutes before IMP administration. The baseline samples will be sent to the clinical laboratory and analyzed using a sensitive and validated assay for glucose measurements. The assay used for primary endpoint glucose measurements should fulfil the requirements of the US FDA Bioanalytical Method Validation Guidance for Industry Section 5 B and C for biomarkers. ⁶ The sampling procedure is described in Section 6.5.3. Before IMP administration, it must be confirmed by the glucose analyzer that the plasma glucose is still ≥70 mg/dL and <90 mg/dL.

If plasma glucose is < 70 mg/dL (3.9 mmol/L), IV glucose solution will be administered to raise plasma glucose to within the 70 to 90 mg/dL (3.9 to 5.0 mmol/L) target range. The run-in period will be adequately extended (at least 30 minutes) until the above target is achieved, the glucose infusion has been discontinued, and new baseline samples for plasma glucose will be collected. In this case, glucose should not be infused within 30 minutes before IMP administration. If plasma glucose is not within the target range after the second attempt, the patient should be rescheduled for a new treatment visit within 7 days (+2 days).

Insulin-Induced Hypoglycemia and Dosing Figure 6-1

Abbreviations: IV=intravenous; PG=plasma glucose

Zealand Pharma A/S

Notes: Patients will be admitted to the clinic with their parent(s)/legal guardian(s) in the night before or at early morning of the dosing day.

If insulin infusion is used; dosing should not be done until at least 5 minutes after infusion is stopped. If glucose infusion is used dosing should not be done until at least 30 minutes after infusion is stopped. Assessments and blood sampling will be performed ongoing from pre-procedure/pre-dose until 300 minutes postdose according to protocol.

Patients will not be allowed to eat or drink (except water) from 4 hours before dosing until 35 minutes after dasiglucagon administration. Patients will only be allowed to eat and drink moderately (appropriate to their body size, with a maximum of 50 grams carbohydrates) starting 35 minutes after IMP administration to minimize discomfort in terms of potential nausea. Two hours after dosing, patients can eat and drink their usual meals. The amount and type of food and drink consumed will be recorded. Patients should remain in bed, to the extent possible, until completion of the test procedure 300 minutes after dosing (bathroom visits are allowed).

6.5.2 Rescue Provisions for Hypoglycemia

During insulin-induced hypoglycemia, plasma glucose levels as well as the patient status will be monitored closely throughout the procedure. After administration of IMP (t=0), if their glucose levels become too low, patients may receive post-treatment IV glucose infusion to ameliorate hypoglycemia, as follows:

- The IV glucose infusion should be initiated if a patient experiences escalating symptoms
 of hypoglycemia (eg, start of moderate symptoms of hypoglycemia) at any time during
 the test procedure. Glucose infusion should then be initiated targeting a plasma glucose
 level >90 mg/dL.
- If plasma glucose is <70 mg/dL between t=8 and t=30 minutes, glucose infusion (eg, 1 to 2 mg/kg administered over 5 to 10 seconds) should be initiated to maintain plasma glucose between 70 mg/dL (inclusive) and 90 mg/dL. Pause glucose infusion if plasma glucose is >90 mg/dL.
- If plasma glucose is <90 mg/dL at t≥30 minutes, glucose infusion (eg, 2 to 3 mg/kg administered over 5 to 10 seconds) should be initiated. Pause glucose infusion when plasma glucose is >90 mg/dL.

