5.1 Inclusion Criteria

Children are eligible to be enrolled in the trial only if all of the following criteria apply:

Age

1. Child must be < 6 years at the time of screening.

Type of Patient and Disease Characteristics

2. Children who are confirmed as having T1D based on medical history and are receiving daily insulin therapy via insulin pump or MDI.

Informed Consent

- 3. Following receipt of verbal and written information about the trial, the parent(s) or legal guardian of the child must be capable of giving signed informed consent before any trial-related activity is carried out as described in Appendix 1 which includes compliance with the requirements and restrictions listed in the informed consent form (ICF) and in this protocol.
- 4. Ability to adhere to the protocol requirements.

Weight

5. Body weight > 8 kg.

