6.5.3 Collection of Blood Samples

The total blood volume to be obtained from any individual child with a body weight of more than 10.0 kg will be about 22.5 mL (see Table 6-3 and Table 6-4 for details). For children with a body weight ≤ 10.0 kg, the frequency of PD (for efficacy) and PK samples will gradually be reduced as specified in Table 6-4 to minimize the blood volume obtained at a single visit (to approximately maximum 1.5% of total blood volume) and over a four-week period (to approximately maximum 3% of total blood volume). These values are within the recommended scope provided by guidelines and based on a child's total blood volume being 75 to 80 mL/kg.⁵

The following blood volume will be taken for each sample at each visit:

Table 6-3 Blood Volumes

Sample type	Visit 1 (mL)	Visit 2 (mL)	Visit 3 (mL)	
Biochemistry	2.00	-	2.00	
Hematology	1.20	-	1.20	
ADA	3.00	-	3.00	
PK*	-	5.00	-	
PD*	-	3.60	-	
Onsite-PG	-	1.50	-	
Sum for each visit	6.2	10.1	6.2	
Total				22.5

Abbreviations: ADA=anti-drug antibodies; Onsite-PG=onsite monitoring of plasma glucose;

Table 6-4 PD (for efficacy) and PK Sampling Based on Body Weight

Body weight at Visit 2	Visit 2	
	PD samples to draw	PK samples to draw
BW> 10.0 kg	pre-dose	pre-dose
	15 min	10 min
	30 min	20 min
		30 min
		40 min
		60 min
		90 min
		140 min
		220 min
		300 min
$10.0 \ge BW > 9.0 \text{ kg}$	pre-dose	pre-dose
	15 min	10 min
	30 min	20 min
		30 min
		40 min
		60 min
		90 min
		140 min
		300 min
$9.0 \ge BW > 8.0 \text{ kg}$	pre-dose	pre-dose
	30 min	10 min
		20 min
		30 min
		40 min
		60 min
		90 min
		140 min
		300 min

Abbreviations: BW=body weight; PD=pharmacodynamics; PK=pharmacokinetics

PD=pharmacodynamics; PK=pharmacokinetics

^{*} Refer to Table 6-4 for details on which PD and PK samples to be collected based on body weight at Visit 1 and Visit 2.

6.6 Continued Access to Trial Intervention After Visit 2

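### The example IV glucose amounts in Protocol 6.5.2, given as the single push described, close a deficit of only a few mg/dL, and the text states no repeat dose or continuing rate

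*Protocol*

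**What the plan says.** Protocol 6.5.2 has three rescue bullets for the period after dasiglucagon. Two of them pair an example amount with a glucose level.

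- **Glucose below 70 mg/dL, 8 to 30 minutes after dosing:** the instruction is "glucose infusion (eg, 1 to 2 mg/kg administered over 5 to 10 seconds) should be initiated to maintain plasma glucose between 70 mg/dL". The upper end of that range is 90 mg/dL, above which the infusion is paused.
- **Glucose below 90 mg/dL from t=30 minutes:** "glucose infusion (eg, 2 to 3 mg/kg administered over 5 to 10 seconds) should be initiated", followed by "Pause glucose infusion when plasma glucose is >90 mg/dL".

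The third bullet is triggered by escalating symptoms. It sets a target above 90 mg/dL but gives no amount, so it is outside this point.

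For a low glucose before dosing, Section 6.5.1 names only a target: "IV glucose solution will be administered to raise plasma glucose to within the 70 to 90 mg/dL" range. It gives no amount per kg.

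The only volume in the documents is total blood volume. It appears in 6.5.1 ("with the total blood volume estimated to be 75 to 80 mL/kg") and again in 6.5.3 ("total blood volume being 75 to 80 mL/kg"). Both places use it to limit blood sampling.

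**The concern.** An example dose should at least show the right order of size for the glucose level it is meant to correct. These two look small for that purpose, and each is described as an amount given within seconds. The bullets do not say that the dose is repeated after a recheck, or that the infusion continues at some rate.

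These are the only rescue amounts in the protocol, and they apply to children under 6 whose glucose has been deliberately lowered. A site that took the example as one complete treatment would under-treat any deficit of more than a few mg/dL until the next glucose check.

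**Working it through.** **Inputs.** Example doses of 1 to 2 and 2 to 3 mg/kg, each over 5 to 10 seconds (6.5.2). Blood volume 75 to 80 mL/kg, that is 0.75 to 0.80 dL/kg (6.5.1, 6.5.3). Two further volumes are assumptions made here to show the range: plasma only, 0.40 to 0.45 dL/kg, and a wider space, 1.5 to 2.5 dL/kg.

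**The plan's own figure.** The protocol states no expected rise per rescue dose. The nearest figure that can be checked is its 1.5% sampling limit: 0.015 × 75 = 1.125 and 0.015 × 80 = 1.20 mL/kg. This agrees with the 1.13 to 1.20 mL/kg in 6.5.1.

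**Rise from one dose** = dose (mg/kg) ÷ volume (dL/kg), counting only the glucose given:

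| Dose | Blood volume | Plasma only (assumed) | Wider space (assumed) |
|---|---|---|---|
| 1 mg/kg | 1.25–1.33 mg/dL | 2.22–2.50 | 0.40–0.67 |
| 2 mg/kg | 2.50–2.67 mg/dL | 4.44–5.00 | 0.80–1.33 |
| 3 mg/kg | 3.75–4.00 mg/dL | 6.67–7.50 | 1.20–2.00 |

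**Where one dose is enough**, on blood volume:

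- To reach 70 mg/dL, from 70 − 2.67 = 67.3 (2 mg/kg) or 70 − 1.25 = 68.8 (1 mg/kg) upward.
- To reach 90 mg/dL, from 90 − 4.00 = 86.0 (3 mg/kg) or 90 − 2.50 = 87.5 (2 mg/kg) upward.
- With plasma only, these starting points become 65.0 to 67.8 and 82.5 to 85.6 mg/dL.

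**Amount needed** = deficit × volume. **Number of example doses** = amount needed ÷ dose:

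| Correction (mg/dL) | Needed on blood volume | Doses, blood volume | Doses, plasma only |
|---|---|---|---|
| 65 to 70 | 3.75–4.0 mg/kg | 1.9–4.0 | 1.0–2.3 |
| 60 to 70 | 7.5–8.0 mg/kg | 3.8–8.0 | 2.0–4.5 |
| 80 to 90 | 7.5–8.0 mg/kg | 2.5–4.0 | 1.3–2.3 |
| 70 to 90 | 15–16 mg/kg | 5.0–8.0 | 2.7–4.5 |

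The first two rows use doses of 1 to 2 mg/kg, the last two 2 to 3 mg/kg. A single dose just covers 65 to 70 mg/dL at the most favourable plasma-only volume. It covers none of the other three corrections at any volume tried.

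**Scale in a small child.** The entry limit is "Body weight > 8 kg". At 8 kg the examples are 8 to 16 mg and 16 to 24 mg of glucose. The blood at 70 mg/dL already holds 8 × 0.75 × 70 = 420 to 8 × 0.80 × 70 = 448 mg.

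**The other reading: continue at the stated speed.** 1 mg/kg over 10 seconds is 6 mg/kg/min, and 2 mg/kg over 5 seconds is 24 mg/kg/min. The later bullet gives 12 to 36 mg/kg/min in the same way. Over a 5-minute check interval this is 30–120 or 60–180 mg/kg. On blood volume the rise is 30 ÷ 0.80 = 37.5 to 120 ÷ 0.75 = 160 mg/dL, or 60 ÷ 0.80 = 75 to 180 ÷ 0.75 = 240 mg/dL. From 60 mg/dL, even the slowest rate ends at 97.5, above the pause level.

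All of these are static figures, not predictions. Dasiglucagon would raise glucose further. Residual insulin, or distribution outside the blood, would lower it.

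**The case against.** The best defence is that the amounts are marked as examples and the governing instruction is to treat to a target. Holding glucose within a range and pausing above 90 mg/dL makes sense only if treatment goes on until that level is reached. On blood volume, 70 to 90 mg/dL needs 15 to 16 mg/kg. At 0.2 to 0.6 mg/kg per second, that takes about 25 to 80 seconds of continued infusion. A clinician who saw glucose still below range would be unlikely to stop after one push.

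Much of this stands. A goal and a stop rule exist, and the targets can be reached by repetition. A reader might infer that rescue under this protocol would fail, or that the amounts are too small in every case. The documents support neither inference: the mismatch belongs to the single-push reading and to deficits larger than a few mg/dL. But the text describes an amount given over seconds, not a rate, and continuing at that speed would overshoot between checks on the same blood volume. One reading under-treats and the other overshoots.

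The safeguards are also real:

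- The glucose analyzer is read about every 5 minutes at or below 110 mg/dL (8.1.2).
- CGM runs alongside (6.5.1), and "additional plasma glucose measurements can be taken at any time during the trial".
- Children are under medical supervision while wearing the sensor (6.1.1).
- The symptom-triggered bullet applies throughout the test procedure.

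They limit the harm without correcting the examples. Section 6.5.1 makes the 5-minute schedule a preference and lets analyzer checks be adjusted for body weight to respect blood limits, so they may be sparser in the smallest children.

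Two limits on the argument are fair. The blood volume was given for sampling, not as a glucose distribution space. The plasma-only case meets this, because it is the most favourable volume tried and any larger space gives a smaller rise. Figure 6-1 was not available for this review, so the statement that no repeat rule is given covers the visible text only.

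**Conclusion.** The point holds. Given as the single push described, the example amounts raise glucose by about 1.3 to 2.7 mg/dL (t=8 to 30) or 2.5 to 4.0 mg/dL (from t=30) on the protocol's blood volume. The maximum is 7.5 mg/dL in an assumed plasma-only space. That corrects a glucose just under the threshold but not 60 to 70, 80 to 90 or 70 to 90 mg/dL. The starting values are illustrative, although children are dosed at 70 to below 90 mg/dL, so a child who has not responded by 30 minutes could plausibly still be in that range.

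A reader might also infer a unit slip. The documents do not show the cause, and none is claimed here. Nor does the point extend to the results. When rescue comes before 30 minutes, the PD sample is taken just before it starts (8.1.2), and the rescue-use endpoints record only whether and when glucose was first given. The matter is one of participant safety and should be fixed, but it does not affect the endpoints or the analysis.

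**What to change.** Delete both example amounts from 6.5.2 and use target-based wording of the kind 6.5.1 already applies before dosing, or replace them with an amount and unit verified by the sponsor's clinical team. In either case, state that glucose is rechecked after each dose and dosing is repeated until the target is reached. No replacement amount is proposed here.

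The cost is an edit to two bullets and a notice to sites before the next child is dosed. The Trial Safety Group's written permission before each dosing (10.1.5.1) is a convenient moment to confirm that the notice has been received, although that step is not described as a route for correcting the protocol. Because the change concerns safety, it may count as a substantial amendment under 10.1.7 and need competent-authority and ethics approval, which would take time. Sample size, endpoints and analysis do not change.
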